## 6.1. Study Intervention(s) Administered

This table lists the interventions used in this clinical study.

Intervention Name	LY3209590	Insulin Degludec	
Туре	Drug	Drug	
Dosage Formulation	Solution	Solution	
Unit Dose Strength(s)	500 units/mL	100 units/mL	
Dosage Levels	Individualized dosing	Individualized dosing	
Frequency of Administration	Once weekly	Once daily	
Routes of Administration	Subcutaneous	Subcutaneous	
Use	Experimental	Active comparator	
IMP	IMP	IMP	
Sourcing	Provided centrally by the sponsor	Provided centrally by the sponsor	

Abbreviation: IMP = Investigational Medicinal Product.

#### Packaging and Labeling

Study interventions will be supplied by the sponsor or its designee in accordance with current Good Manufacturing Practice. Study interventions will be labeled as appropriate for country requirements.

## 6.1.1. Medical Devices

- 1. Provided for use in this study are the prefilled pen injectors, for the delivery and administration of either LY3209590 or insulin degludec.
- 2. Instructions for device use and storage requirements are provided in the "Instructions for Use."
- 3. All Product Complaints, including malfunction, use error, and inadequate labeling, shall be documented and reported by the investigator throughout the study (see Section 8.3) and appropriately managed by the sponsor.

## 6.1.2. LY3209590 and Insulin Degludec Dosing

## Frequency of Dosing with LY3209590 and Insulin Degludec

LY3209590 will be administered once weekly at approximately the same time and day each week using an insulin-prefilled pen (with 5-unit increments). If a dose is missed, it should be administered as soon as possible if at least 3 days (72 hours) remain until the next scheduled dose. If an interval of less than 3 days remains before the next scheduled dose, the missed dose should be skipped and the next dose should be administered on the regularly scheduled day. In each case, participants can then resume their regular once-weekly dosing schedule. The day of weekly administration can be changed, if necessary, as long as the last dose has been administered at least 3 days earlier.

Insulin degludec (U100) will be administered daily at approximately the same time each day using commercially available insulin-prefilled pens (with 1-unit increments).

## Maximum Units of Dosing with LY3209590 and Insulin Degludec

For LY3209590, the maximum number of units per injection in the LY3209590-prefilled pen is 400 units. Doses greater than 400-units a week (approximately 57-units per day of basal insulin  $[57 \times 7 \text{ days} = 399]$ ) will require more than 1 injection. The maximum one-time loading dose for this study is 1600-units, and the maximum weekly dose is 1400-units. The maximum doses are supported by the current product safety assessment.

For insulin degludec, the maximum number of units per injection of insulin degludec (U100) is 80 units. For participants who require >80-units per day, more than 1 injection will be required to administer the full daily dose of insulin degludec.

## **Anatomical Location of Injections**

For both treatments, participants will be instructed to rotate injection sites from one injection to the next, even when injecting within the same region. Injections may be administered in the abdomen, thigh, arm, or buttock. Refer to the IFU for complete instructions on dose administration.

## 6.1.3. General Insulin Dose Considerations for Both Treatment Groups

## **Transition to Study Insulins**

The participants' initial and weekly dose of LY3209590 or daily dose of insulin degludec will be determined based on the participant's usual daily basal insulin dose prior to randomization. The starting doses take into consideration the prestudy basal insulin's label with regards to the ability

to do unit-to-unit conversions across insulin types/regimens. For participants whose prestudy basal insulin regimens are typically adjusted to the more conventional once-daily (U-100) basal insulin regimens (for example, twice-daily NPH or once-daily U-300 glargine), the total daily dose is reduced by 20% before multiplying by 7 to obtain the weekly dose equivalent.

The dosing and titration algorithms to be used will be based on the participant's treatment assignment to either LY3209590 or insulin degludec as described in Sections 6.1.4 and 6.1.5 respectively. Participants will be instructed to not take their prestudy basal insulin on the day of randomization since they will be dosed at the site with the allocated study insulin.

## **Insulin Dose Titration and Dose Maintenance**

In this treat-to-target study, both treatment groups will undergo titration to achieve and maintain an FBG target within the range of 80-120 mg/dL (4.4-6.6 mmol/L). Active titration will occur in both treatment groups between Visits 3 to 15 (Weeks 0 to 12) which will be designated as the Titration Period with the goal to achieve insulin dose stabilization by Visit 15 (Week 12) with a minimum of monthly adjustments as necessary during the Maintenance Period from Visit 15 to 37 (Weeks 12 to 78).

Using the e-diary-linked study-provided glucometer, participants in both treatment groups will perform daily self-monitored FBGs. A minimum of 3 FBG readings on separate days each week must be obtained so that investigators can review the data to make dose adjustments using the titration algorithms for once-weekly or once-daily insulins (Sections 6.1.4 and 6.1.5). The median FBG to use in determining the dose adjustments starting at Visit 5 (Week 2) is obtained from the 3 most recent FBGs in the previous week. The median is the middle value when the 3 values are placed in ascending or descending order. For example, if a participant's FBGs for the past 3 consecutive measurements were 180, 202, and 190, the median is 190.

**Note:** If the participant has only 2 FBG readings for the week, then the lesser of the readings should be used to determine the dose adjustments. If only 1 FBG measurement is available, determination if dose is changed using only a single FBG value is at the discretion of the investigator.

When considering any dose adjustments (in either treatment group), the investigator will review whether the participant experienced any documented episodes of hypoglycemia. If the participant experienced any documented BG  $\leq$ 70 mg/dL ( $\leq$ 3.9 mmol/L) in the previous week, the dose should not be increased. If criteria for hypoglycemia dose reduction are met, the prior week's basal dose is decreased according to the treatment as indicated in the Hypoglycemia Dose Reduction Criteria for LY3209590 or the Hypoglycemia Dose Reduction Criteria for Insulin Degludec tables below. Investigators are expected to follow the dosing algorithms for the protocol; however, modifications of the basal insulin dose may be influenced by other clinical circumstances or safety considerations known to the investigator. If the investigator prescribes a dose other than the algorithm recommended dose, the investigator is responsible for documenting the clinical rationale for the prescribed dose in the Study Works web portal.

## 6.1.4. LY3209590 Dose Initiation and Modification

In this section, dosing instructions for LY3209590 are provided for

• dose initiation at Visit 3 (Week 0)

- administration of the weekly dose at Visit 4 (Week 1), and
- dose titration beginning at Visit 5 (Week 2) and continuing throughout the treatment period.

**Note:** The first dose is administered by site personnel; subsequent doses are self-administered.

## Visit 3 – (Week 0): Randomization Visit

Determine the median FBG from the week prior to randomization (Visit 3 [Week 0])

Follow instructions in the LY3209590 Loading Dose Calculation table below for participants with FBG >120 mg/dL (6.6 mmol/L)

Follow instructions in the LY3209590 Starting Weekly Dose Calculation table below for participants with FBG  $\leq 120 \text{ mg/dL}$  (6.6 mmol/L)

**Note:** If a participant is on NPH twice-daily or U300 glargine, the prestudy basal insulin dose should be reduced by 20% when determining Usual Daily Dose of the prestudy basal insulin before calculating the Starting Weekly Dose.

## LY3209590 Loading Dose Calculation –Participants with FBG >120 mg/dL (6.6 mmol/L)

Step	Action	Example Participant A (FBG >120 mg/dL [6.6 mmol/L])
1.	Determine usual prior daily basal dose from lead-in period	30 units/day
2.	Calculate Starting Weekly Dose (Usual Daily Dose multiplied by 7 and round to nearest 10)	210 units/Week
3.	Multiply Starting Weekly Dose by 3 to determine the Loading Dose a	630 units Loading Dose

a The Loading Dose should not exceed a dose of 1600 units.

If the calculated Loading Dose is >1600 units, the maximum loading dose of 1600 units is given as the one-time dose at Visit 3 (Week 0).

# LY3209590 Starting Weekly Dose Calculation – Participants with FBG ≤120 mg/dL (6.6 mmol/L)

Step	Action	Example Participant B (FBG ≤120 mg/dL
		[6.6 mmol/L])
1.	Review usual prior daily basal dose from lead-in period	30 units/day
2.	Calculate Starting Weekly Dose	210 units/Week
	

(Usual Daily Dose multiplied by 7 and round to nearest 10)

	

The maximum weekly dose should not exceed 1400 units. If the calculated weekly dose is greater than 1400 units, prescribe only 1400 units.

## Visit 4 (Week 1): Starting Weekly Dose

If the participant experienced hypoglycemia in the previous week and met any of the criteria for a dose reduction listed in the Hypoglycemia Dose Reduction for LY3209590 table below,

## CONFIDENTIAL

subtract 40 units from the **Starting Weekly Dose** to obtain the dose for administration at Visit 4 (Week 1).

If the Hypoglycemia Dose Reduction criteria are not met, administer the Starting Weekly Dose.

# CAUTION: DO NOT REPEAT ADMINISTRATION OF THE LOADING DOSE

## Hypoglycemia Dose Reduction for LY3209590

Hypoglycemia Dose Reduction Criteria Based on BG Values	Unit Dose Decrease
$\geq$ 3 episodes $\leq$ 70 mg/dL (3.9 mmol/L)	
$\geq$ 1 nocturnal episode $\leq$ 70 mg/dL (3.9 mmol/L)	40 units
$\geq$ 1 episode <54 mg/dL (3.0 mmol/L)	To units
Any confirmed severe hypoglycemia	

The following steps illustrate an example calculation for Visit 4 (Week 1) of Starting Weekly Dose.

Step	Action	Example Participant B
1.	Review Starting Weekly Dose from Visit 3 (Week 0) calculations	210 units/day
2.	Determine if any of Hypoglycemia Dose Reduction criteria are met in prior week: If yes, subtract 40 units from Starting Weekly Dose If not, administer Starting Weekly Dose	
 
a. If a Hypoglycemia Dose Reduction criterion is met,
 
➤ Week 1 Dose = 210 - 40 = 170 units/week
 
b. If no Hypoglycemia Dose Reduction criterion was met, the Week 1 Dose=210 units/week
 

## Visit 5 (Week 2): Titration to Week 77

If the participant experienced any documented hypoglycemia (BG  $\leq$ 70 mg/dL [3.9 mmol/L]) in the previous week, the dose should not be increased.

If the participant experienced hypoglycemia in the previous week and met criterion for a dose reduction as described in the Hypoglycemia Dose Reduction for LY3209590 table above, subtract 40 units from the previous weekly dose.

If no BG  $\leq$ 70 mg/dL (3.9 mmol/L) was reported, use the median FBG from the previous week to obtain the dose adjustment from the titration algorithm in the LY3209590 Dose Adjustment Based on Median FBG table below. If participant's median FBG from the week prior to randomization is  $\leq$ 120 mg/dL (6.6 mmol/L) or prestudy basal insulin dose <20 units/day as described below, use dose adjustments that correspond to that column. If the median FBG is within the target range from 80 to 120 mg/dL (4.4 to 6.6 mmol/L) inclusive, no change would be made to the dose from the previous week.

Median FBG		LY3209590 Dose Adjustment Units (U)			
mg/dL	mmol/L	When Median FBG ≤120 mg/dL (6.6 mmol/L) or Prestudy Basal Insulin Dose <20 U	When Median FBG >120 mg/dL (6.6 mmol/L) Units		
<80	<4.4	(–) 20 U	(–) 20 U		
80-120	4.4–6.6	No change to dose	No change to dose		
121–140	6.7–7.7	(+) 10 U	(+) 20 U		
>140	>7.7	(+) 20 U (+) 40 U			

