## Justification for the insulin degludec starting dose

The starting dose for insulin degludec (U100) is the same as the daily dose of basal insulin the participant was taking prior to Visit 3 (Week 0). Insulin degludec will be titrated to achieve FBG target of 80-120 mg/dL (4.4-6.6 mmol/L) using an algorithm that is patterned after the well-established Riddle algorithm and other published algorithms (Meneghini et al. 2007, Kadowaki et al. 2017) but modified to balance efficacy and hypoglycemia for the same FBG targets as LY3209590 (Section 6.1).

Safety of study participants will be closely monitored during the early stages of dose titration to determine whether adjustments to the dose are needed to safely achieve FBG targets of 80-120 mg/dL (4.4-6.6 mmol/L) and will continue throughout the study (See Section 6.1).

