## Site Responsibilities Related to Study Drugs

The investigator or their designee is responsible for the following:

- explaining the correct use and storage of the study drug to the participant and verifying those instructions are followed properly
- using the dosing algorithm to assess and titrate the doses weekly for the first 12 weeks and at least monthly throughout the remainder of the study
- maintaining accurate records of IP dispensing, and
- collecting of all unused study medication at the end of the study, returning it to Lilly, or designee, unless the sponsor and sites have agreed all unused medication is to be destroyed by the site, as allowed by local law.

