## Visit 4 (Week 1) to Visit 37 (Week 78)

If the participant experienced any documented hypoglycemia (BG  $\leq$ 70 mg/dL [3.9 mmol/L]) in the previous week, the dose should not be increased.

If the participant experienced hypoglycemia in the previous week that met dose reduction criterion, decrease the daily dose as described in the Hypoglycemia Dose Reduction Criteria for Insulin Degludec table below.

Hypoglycemia Dose Reduction Criteria	Unit Dose Decrease
Based on BG Values	
$\geq$ 3 episodes of $\leq$ 70 mg/dL ( $\leq$ 3.9 mmol/L)	
$\geq$ 1 nocturnal episode $\leq$ 70 mg/dL (3.9 mmol/L)	2–6 units a
$\geq$ 1 episode <54 mg/dL (3.0 mmol/L)	2-0 units
Any confirmed severe hypoglycemia	

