## Hypoglycemia Dose Reduction Criteria for Insulin Degludec

a Dose reductions of 2 or 4 units may occur every 3 days to achieve a gradual weekly reduction of 6 units as clinically indicated.

If hypoglycemia dose reduction criteria are not met, use the median FBG from the previous week to obtain the dose adjustment from the titration algorithm in the Insulin Degludec Dose Adjustment table below. If the median FBG is within the target range from 80 to 120 mg/dL (4.4 to 6.6 mmol/L), no change would be made to the dose from the previous week.

Median FBG		Insulin Degludec Dose Adjustment	
mg/dL	mmol/L	units	
<80	<4.4	(-) 3 units (decrease)	
80-120	4.4-6.6	No change	
121-140	6.7-7.7	(+) 3 units (increase)	
>140	>7.7	(+) 6 units (increase)	

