6.2. Appendix 2: Treatment Compliance

Treatment compliance will be summarized using the mITT population, excluding inadvertently enrolled participants.

The study protocol provides dosing algorithm for both study treatments. The investigator will calculate algorithm recommended dose based on the participant fasting blood glucose and hypoglycemia occurrence reported in e-diary. If the investigator does not agree with the algorithm recommended dose, the investigator will prescribe another dose for the participant and choose the reason of not following the algorithm recommended doses different from a pre specified list of terms. The number and percentage of investigator prescribed doses different from algorithm recommended doses will be provided to evaluate the adherence to the algorithm dose. The reason for not following the algorithm recommended dose will also be summarized.

The first dose of study treatment is administered by site personnel and the subsequent doses are self-administered. The number and percentage of investigator prescribed doses that are not equal to participant administered dose will be provided.

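### After one or two daytime readings of 54–70 mg/dL with median FBG below 80, degludec is cut 3 units/day but the LY3209590 algorithm states no decrease, although higher readings give −20 units/week

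*Protocol*

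**What the plan says.** Protocol Section 6.1.3 sets a rule common to both arms: "When considering any dose adjustments (in either treatment group), the investigator will review whether the participant experienced any documented episodes of hypoglycemia". Any reading at or below 70 mg/dL in the previous week rules out an increase. Section 6.1.5 repeats this for degludec ("in the previous week, the dose should not be increased"), and Section 6.1.4 does the same for LY3209590.

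Both arms also use the same four reduction criteria: three or more episodes at or below 70, any nocturnal episode at or below 70, any episode below 54, or confirmed severe hypoglycemia. If one is met, the LY3209590 instruction is "subtract 40 units from the previous weekly dose"; degludec is reduced by 2–6 units.

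The arms part when no criterion is met:

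- **LY3209590 (Section 6.1.4, from Visit 5):** if no BG at or below 70 "was reported, use the median FBG from the previous week to obtain the dose adjustment from the titration algorithm in the LY3209590 Dose Adjustment" table. A median below 80 gives −20 units/week in both columns.
- **Degludec (Section 6.1.5):** "If hypoglycemia dose reduction criteria are not met, use the median FBG from the previous week to obtain the dose adjustment". A median below 80 gives −3 units on the daily dose.

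Section 4.3 describes the degludec algorithm as patterned on published ones "but modified to balance efficacy and hypoglycemia for the same FBG targets as LY3209590". Section 6 asks sites to "assess and titrate the doses weekly for the first 12 weeks and at least monthly throughout the remainder of the study". SAP Section 6.2 plans a compliance summary: "The number and percentage of investigator prescribed doses different from algorithm recommended doses will be provided to evaluate the adherence to the algorithm dose".

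**The concern.** One or two non-nocturnal readings of 54–70 meet none of the reduction criteria. In such a week the degludec participant still reaches the table, and the LY3209590 participant does not. If median FBG is below 80, degludec has a prescribed decrease and LY3209590 has none.

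Three things are at stake.

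- **Safety ordering.** An LY3209590 participant who recorded a low reading gets a weaker stated instruction than one who did not. This is the arm whose insulin has a half-life of about 17 days, so an excess dose is slow to clear.
- **Duration.** After Week 26 many scheduled visits are four weeks apart, and Weeks 52 and 60 are eight weeks apart. An omitted decrease can then stand for several weeks.
- **Adherence reporting.** If the dose-calculation tool follows the written conditions, a sensible decrease in this situation is a departure from the algorithm for LY3209590 and adherent for degludec. The percentages in the SAP compliance summary would then not mean the same thing in the two arms.

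**Working it through.** **Inputs.** The reduction criteria, entry conditions and table values come from Protocol Sections 6.1.3 to 6.1.5. The nocturnal window, midnight to 6 AM, comes from Section 8.3.3. As a check on the reading of the rules, the protocol's own Visit 4 example reproduces: 210 − 40 = 170 units/week.

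**Step 1: apply the written rules to example weeks.** Each week has three FBGs, all after 6 AM. Degludec per week = 3 units/day × 7 = 21 units.

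| FBG (mg/dL) | Median | Readings ≤70 | Criterion met | LY3209590 per week | Degludec |
|---|---|---|---|---|---|
| 72/76/78 | 76 | 0 | no | −20 | −3/day (−21/week) |
| 68/76/78 | 76 | 1 | no | no increase; no decrease stated | −3/day (−21/week) |
| 66/68/78 | 68 | 2 | no | no increase; no decrease stated | −3/day (−21/week) |
| 66/68/70 | 68 | 3 | yes | −40 | −2 to −6 units |

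Reading down the LY3209590 column as glucose falls, the stated action goes from −20 to nothing stated (twice) and then to −40. It is not monotone. The degludec column has no such break. With 65/95/100 (median 95) neither arm changes dose, so the gap is confined to a median below 80 with one or two non-nocturnal readings of 54–70.

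**Step 2: how often this could occur.** The documents give no daily FBG distribution, so these are assumptions: independent normal readings, SD 8, 10 or 12 mg/dL, three or seven readings a week, all after 6 AM, and 400,000 simulated weeks per setting. A week counts if the median of the last three readings is below 80, one or two readings are at or below 70, and none is below 54.

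| True mean FBG | Share of all weeks |
|---|---|
| 80 | 20–31% |
| 85 | 4–16% |
| 90 | 0.4–5% |
| 95 | about 1% or less |
| 100 | under 0.2% |

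Among weeks with median below 80, at means of 80 to 90, no decrease is stated in roughly 11–63%.

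**Step 3: one setting in full.** Mean 85, SD 10, seven readings: 22.6% of weeks have a median below 80. Of these, 10.3 points get −20 units, 11.6 points get no stated decrease, and the remaining 22.6 − 10.3 − 11.6 = 0.7 points meet a criterion and get −40.

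**Step 4: means below target.** At a mean of 75 the share is 47–52% with three readings and 27–48% with seven. At a mean of 70 it is about 51–68% with three readings. With seven readings at that mean, the −40 criteria already fire in 79–84% of weeks.

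FBGs taken before 6 AM would count as nocturnal and shrink all these shares. Non-fasting readings were not modelled.

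**The case against.** The strongest reply is that the LY3209590 text is silent and does not instruct a hold. Barring an increase leaves a decrease open, both arms are titrated to 80–120 mg/dL, and Section 6.1.3 lets the investigator depart from the algorithm with a documented rationale. This is right as far as it goes. It is why the point is put as no decrease stated, and it softens the practical effect. It does not supply the missing rule, and sites may read the silence differently.

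Second, a participant with a true mean of 85 or 90 is in target, so a median below 80 is partly sampling noise and a missed 20-unit cut is not clearly harmful. That is fair. But the same sampling noise triggers a cut for degludec, and for LY3209590 participants with no low reading. The situation also remains common at means of 70 to 75 when only three readings are available.

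Third, dose review is scheduled every two weeks between Weeks 12 and 26, and sites can see the diary data at any time. A long-standing omission is therefore mainly a concern after Week 26.

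Fourth, the tool's logic is not in the documents, and the SAP summary is descriptive and tabulates reasons for departures. The adherence point is therefore conditional and affects no test.

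**Conclusion.** The concern holds. The mismatch and the broken ordering follow from the text alone and need no assumption: in this situation no decrease is stated for LY3209590 against −21 units/week for degludec, while an LY3209590 participant with no reading at or below 70 gets −20. No other provision in the protocol fills the gap.

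How often it occurs rests on the assumed FBG distribution. It is appreciable for participants at or near the lower end of target and rare in the middle of the range. No trial-level frequency can be derived from the documents. The gap applies to LY3209590 from Visit 5. It excludes nocturnal readings at or below 70, readings below 54 and severe events, and no effect on HbA1c, the nocturnal hypoglycemia endpoint or power is claimed. It should be fixed because the written rule is less cautious at lower glucose for the longer-acting insulin, and because the recommended dose differs by arm without a stated reason.

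**What to change.** - In Section 6.1.4, replace the condition that no BG at or below 70 was reported with the degludec condition that the reduction criteria are not met. Keep the bar on any increase after such a reading. The weekly cuts in this situation become 20 and 21 units, and the LY3209590 ordering is restored.
- In Section 6.1.5, add a sentence that the bar on increases overrides the increases in the table.
- Check that the dose-calculation tool uses the same logic, so that the algorithm-recommended dose in SAP Section 6.2 means the same in both arms.

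Narrowing the degludec condition instead would match the arms but leave both out of order.

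The text change is one clause and one sentence, plus the tool check. It needs a protocol amendment with ethics approval, and health-authority approval if judged substantial (Section 10.1.1). Visits, data collection and sample size do not change.
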